## Objectives\*

Aim 1. Determine if non-invasive Adhear is an equally effective treatment solution for unilateral profound sensorineural hearing loss when compared to invasive boneanchored implants.

Hypothesis: We hypothesize that non-invasive Adhear bone conduction technology will provide similar benefit to the more invasive bone anchored implant system for unilateral profound sensorineural hearing loss.

Aim 2. Non-invasive Adhear is an equally effective treatment solution for conductivehearing loss when compared to invasive bone anchored implants.

Hypothesis: We hypothesize that non-invasive Adhear bone conduction technology will provide similar benefit to the more invasive bone anchored implant system for conductive hearing loss.

Aim 3. Non-invasive Adhear is a more effective treatment solution for pediatric hearing loss when compared to bone conduction devices worn on a headband.

Hypothesis: We hypothesize that non-invasive Adhear bone conduction technology will increase objective and subjective benefit when compared to traditional bone anchored implant processors worn on a headband for pediatric conductive hearingloss.

Aim 3a. - To evaluate the validity of the non-invasive ADHEAR bone conduction hearing system in children with bilateral or unilateral conductive hearing loss

Aim 3b. To compare the benefits of the non-invasive ADHEAR bone conduction hearing system in children with bilateral and unilateral conductive hearing loss to traditional non- invasive bone conduction hearing systems worn on a headband.

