**Objective and behavioral outcome measures unilateral conductive hearing loss subjects:**

- Data logging of device use (parent and subject report)
- Soundfield aided narrowband signal thresholds – better ear plugged
- Soundfield aided Ling thresholds – better ear plugged using the DSLio - Ling 6(HL) test (v2.0) which provides calibrated, pre-recorded Ling 6 sounds (m, u, a, i, sh, s) for use in measuring unaided or aided thresholds.
- Soundfield aided speech reception thresholds using Calibrated and pre-recorded Auditec Spondee lists– better ear plugged
- Word recognition ability using the Auditec Inc PBK-50 words. The majority of subjects enrolled are expected to be between the ages of 3 and 7 and the PBK word list offers the most age appropriate assessment of word recognition ability for this age group, while also allowing for accurate assessment of audibility in older children under aided condition. In those children who are not able to repeat words reliably, a detection

task will be conducted. Tests will be conducted in the soundfield with the better ear plugged for soft (35 dB) and average (50 dB) speech inputs at speech front, noise front (0°/0° azimuth)

- Aim 3b

Pediatric bilateral conductive hearing loss patients who are between the ages of 2 and 17 years of age and are currently managed by the UMEI with a bone conduction device attached to a softband will be enrolled for study. Subjects will be given the ADHEAR bone conduction system on trial for 4 weeks ± 7 days. Subjects will be evaluated over 3-4 experimental visits.

- VISIT 1: Assessment of subject's bone conduction device on softband and initiation of ADHEAR trial
  - Prior to dispensing of the experimental system, function of the subject's current bone conduction device will be verified.
  - Subjective measures will be administered to determine benefit and satisfaction with the subject's own device on the softband.
  - Subjects will undergo behavioral measures of benefit with own bone conduction device on a softband. It is anticipated that the majority of bilateral conductive hearing loss subjects will be unilaterally fitted. Subjects will be tested in their everyday listening condition
  - Subjects will be provided ADHEAR bone conduction hearing system unilaterally
  - In those who are bilaterally fit with a bone conduction device, testing will be conducted unilaterally. To maintain the child's everyday listening condition, participants will be fit with 2 ADHEARs (i.e. bilateral). T

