- VISIT 2 (2 weeks ± 90 days):
  - Subjective measures will be administered to determine benefit and satisfaction with the ADHEAR bone conduction hearing system
  - Subjects will undergo behavioral measures of benefit with ADHEAR bone conduction hearing system unilaterally
  - Subjects will be provided ADHEAR bone conduction hearing system bilaterally
  - In those who are bilaterally fit at time of enrollment, testing will be conducted bilaterally with the ADHEARs, and trial will discontinue.
- VISIT 3 (4 weeks ± 90 days):
  - Subjective measures will be administered to determine benefit and satisfaction with the ADHEAR bone conduction hearing system
  - Subjects will undergo behavioral measures of benefit with ADHEAR bone conduction hearing system bilaterally
  - Time and subject permitting subjects will be tested in bilateral softband condition, otherwise this will be completed in an additional visit (4)

Objective and behavioral outcome measures bilateral conductive hearing loss subjects:

- Data logging of device use (parent and subject report)
- Soundfield aided narrowband signal thresholds bilaterally aided
- Soundfield aided Ling thresholds using the DSLio - Ling 6(HL) test (v2.0) which provides calibrated, pre-recorded Ling 6 sounds (m, u, a, i, sh, s) for use in measuring unaided or aided thresholds.
- Soundfield aided speech reception thresholds
- Word recognition ability using the Auditec Inc PBK-50 words under bilaterally aided conditions. Tests will be conducted in the soundfield with the better earplugged for

soft (35 dB) and average (50 dB) speech inputs at speech front, noise front (0°/0° azimuth)

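### Aim 3b's bilateral ADHEAR versus bilateral softband comparison confounds device with bilateral experience, test order and, for some children, test day; the direction of any bias is unknown

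*Combined protocol and SAP*

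**What the plan says.** Under Objectives, Aim 3b is "To compare the benefits of the non-invasive ADHEAR bone conduction hearing system in children with bilateral and unilateral conductive hearing loss" against headband-worn systems. The Aim 3b part of Study Design then sets out a fixed sequence.

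- **Visit 1.** The child's own softband device is assessed: "It is anticipated that the majority of bilateral conductive hearing loss subjects will be unilaterally fitted", and "Subjects will be tested in their everyday listening condition". For the others, "In those who are bilaterally fit with a bone conduction device, testing will be conducted unilaterally".
- **Visit 2**, given as "VISIT 2 (2 weeks ± 90 days". ADHEAR is tested on one side. Then: "Subjects will be provided ADHEAR bone conduction hearing system bilaterally". For children who came with two devices: "In those who are bilaterally fit at time of enrollment, testing will be conducted bilaterally with the ADHEARs, and trial will discontinue".
- **Visit 3**, at 4 weeks with the same 90-day window. Bilateral ADHEAR is tested. The bilateral softband line follows: "Time and subject permitting subjects will be tested in bilateral softband condition, otherwise this will be completed in an additional visit (4". No wear period is given for the bilateral softband, and no interval to Visit 4.

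The introduction to Aim 3b limits the ADHEAR trial to 4 weeks with a 7-day tolerance. Data Management names Student's t-tests or Wilcoxon signed rank tests at the 0.05 level, with no term for order, visit or experience.

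**The concern.** A paired comparison isolates the device only if the two conditions differ in nothing else that affects the score. Here they differ in three further ways. ADHEAR has been worn on both sides at home, while no such period is stated for the softband. The softband is always tested after ADHEAR. For some children it is also tested on another day, and the child's state or the clock decides which.

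On the legible text this is the only comparison that matches two ADHEARs with two softband devices. Children fitted bilaterally at enrolment are tested on one side at Visit 1 and leave after the bilateral ADHEAR test at Visit 2, so they contribute no bilateral softband score. Whatever Aim 3b concludes about bilateral fitting rests on this contrast. A difference could appear between equivalent devices, or a real one could be masked, and a larger sample would not help.

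The protocol controls order elsewhere: Aims 1 and 2 randomise conditions by subject, and Aim 3 assigns the first device at random. Aim 3b does neither and gives no reason.

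**Working it through.** The plan states no power, SD, margin or effect size for Aim 3b, so there is no figure of its own to reproduce. Three checks were made.

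**1. Wear before the bilateral tests.** Bilateral ADHEAR wear = Visit 3 day − Visit 2 day, with days before 0 set to 0.

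- Nominal: 28 − 14 = 14 days.
- With the 90-day windows: Visit 2 falls on days 0 to 104 (14 + 90) and Visit 3 on days 0 to 118 (28 + 90). Wear can be 0 to 118 days.
- If the 7-day tolerance governs the end of the trial: Visit 3 falls on days 21 to 35, so wear is 0 to 35 days.
- Bilateral softband: no wear stated.

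**2. What the contrast estimates.** Let

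- d = true device difference (ADHEAR − softband);
- e = net effect of unequal experience with the two conditions, of either sign;
- p = effect of being tested second in a session rather than first (negative for fatigue, positive for practice);
- v = effect of being tested at Visit 4 rather than first at Visit 3;
- q = share of children whose softband test moves to Visit 4.

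As planned, the expected paired difference is d + e − (1 − q)p − qv. Every child has ADHEAR first, so no data exist from which p or v could be estimated apart from d. Adding model terms would not help.

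With both tests in one session and equal numbers in each order, the two orders give d + e − p and d + e + p. Their mean is d + e. Order and visit drop out; experience does not.

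**3. Illustration of size.** Inputs: two-sided paired t-test at 0.05 (sidedness is not stated, so this is assumed), d = 0, and an assumed net bias b in SDs of the paired difference. The test statistic is noncentral t with n − 1 degrees of freedom and noncentrality b√n; for n = 10 and b = 0.5 that is 0.5 × 3.16 = 1.58. Study Populations sets a minimum of 10 children with bilateral loss. Those fitted bilaterally leave at Visit 2, so fewer may reach this contrast; n = 6 and 8 are also shown.

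| Assumed net bias b | n = 6 | n = 8 | n = 10 |
|---|---|---|---|
| 0 | 2.5% | 2.5% | 2.5% |
| 0.25 | 7.3% | 8.9% | 10.6% |
| 0.5 | 16.9% | 23.1% | 29.3% |
| 0.8 | 35.6% | 49.6% | 61.6% |

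Each entry is the chance of a significant result in the direction of the bias. A positive b favours ADHEAR. The figures are symmetric: at n = 10, b = −0.25 and −0.5 give 10.6% and 29.3% in favour of the softband. The documents support no particular value or sign of b.

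**The case against.** A reader might infer that the design tilts the result toward ADHEAR. Lack of acclimatization to two softband devices, and fatigue when they are tested last in a session, would act that way. Other forces oppose them:

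- the softband test follows three earlier batteries and the bilateral ADHEAR test only two, so practice would favour the softband;
- bilateral listening learned with two ADHEARs may carry over;
- these children are established softband users, and ADHEAR is new to them;
- the Visit 4 option is itself a safeguard against same-day fatigue.

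Aided thresholds may also depend less on acclimatization than word recognition does. This objection stands: the sign cannot be determined.

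A reader might also infer that most of these children have never worn two softband devices. The protocol gives their expected current fitting, not their history, so this is not established.

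Nor is all of Aim 3b's device comparison lost. For children fitted on one side, own softband at Visit 1 against one ADHEAR at Visit 2 matches the number of devices. There the softband is the more experienced device and is tested first. The point here is confined to bilateral fitting.

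Finally, calling this the only bilateral comparison depends on the Visit 1 text, which mentions both the everyday listening condition and unilateral testing for bilaterally fitted children, in a bullet that breaks off. If those children were in fact tested with both devices at Visit 1, a second bilateral comparison would exist, again with the softband more familiar and tested first. That would not remove the confounding at Visits 3 and 4.

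**Conclusion.** The concern holds as confounding of unknown direction. For children fitted unilaterally at enrolment, device is inseparable from bilateral experience (nominally 14 days against none stated), from position (softband after ADHEAR in every child) and, for some, from test day. No analysis of data collected this way can separate them. The documents do not support a claim of bias in ADHEAR's favour, and the probabilities above are conditional on assumed values of b.

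The conclusion rests on the legible Visit 1 and Visit 2 text and on reading the Visit 3 list as the order of testing. It affects one part of one sub-aim, but it is cheap to repair before testing and cannot be repaired afterwards.

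**What to change.** 1. Randomise by child, in balanced numbers, the order of the bilateral ADHEAR and bilateral softband tests, as Aims 1 and 2 already do for their conditions.
2. Run both in the same session. If both do not fit at Visit 3, do both at the additional visit already allowed, rather than splitting them across days. State the interval to that visit.
3. Record the test visit, the order, and prior bilateral experience with each device. Data Management already lists prior hearing treatment and hours of use, but nothing specific to bilateral wear.
4. Random order does not equalise wear (the e term remains). Report the contrast as bilateral ADHEAR after take-home use against bilateral softband at first fit, not as evidence that one device is superior.
5. Reconcile the 7-day trial tolerance with the 90-day visit windows, and clarify how bilaterally fitted children are tested at Visit 1.

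A first-fit comparison of both devices at Visit 2 is optional. It would reduce the difference in bilateral experience, but it puts three batteries into one session for young children, who will also have just worn one ADHEAR for nominally two weeks.

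Cost: protocol wording, a randomisation list, slightly more scheduling work, and some children using the extra visit for both batteries instead of one.

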#### Subjective outcome measures

*In light of COVID-19 restrictions, the subjective questionnaires will be collected over the phone given that the subjects and/or guardian cannot come into the clinic. A verbal addendum will be read to the participant(s) over the phone to confirm they agree with the new changes. The questionnaires will be administered after participant gives verbal consent.*

Subjective questionnaires (included in this submission) will be administered prior to and at the end of each phase to the subject. A parent proxy of the subjects questionnaire will also be administered to the subjects guardian to gauge parent/guardian perception of benefit with bone conduction technology. These subjective questionnaires will be given pre- and post-evaluation to both the subject and his/her guardian in order to determine the impact of bone conduction technology on subject and guardian perceptions of benefit. The pediatric questionnaire uses images to help ensure the child understands the response choices. Additionally both the child and the guardian will fill out the questionnaire with a study team member present so that they may ask for clarification if/when necessary. For the pediatric questionnaire 2 practice questions are included to ensure the child understands the question and response format and is capable of completing the questionnaire reliably. Note that the questionnaire given prior to assignment of a device will include only questions 1 - 15 for the guardian version and only questions 1 - 18 for the pediatric version since the remaining questions are device-specific. The unabridged full version of the questionnaire will be administered at both the end of phase 1 and phase 2.

## **Data and Specimen Banking\***

All the previously described data will be stored on the PI's computer and used for analyses purposes in room 526 of the clinical research building at the University of Miami Medical Center located at [name]. It will be password protected, and unique identifiers used for subject protection. Data will not be distributed, except in the form of peer-reviewed publication or oral presentation maintain the confidentiality of the subjects.

## **Data Management\***

Data collected includes: Gender, age, language, etiology and type of hearing loss, treatment ear, audiometric data including thresholds and speech outcomes, prior hearing treatment, date of activation or device use, aided thresholds, aided speech in noise performance, hours of device use, and subjective outcomes (see questionnaires included).

All the previously described data will be stored on the PI's computer and used for analyses purposes in room 526 of the clinical research building at the University of Miami Medical Center located at [name]. It will be password protected, and unique identifiers will be used for subject protection. Descriptive statistics will be used to report demographic (e.g. age and

gender) data. Quantitative data will be presented as mean, standard deviation (SD) and range (minimum and maximum); qualitative data will be presented as frequencies and percentages. Inferential statistics will be applied to detect differences in speech in noise performance as a function of transcranial attenuation. For this purpose, parametric Student's t-tests or nonparametric Wilcoxon signed rank tests will be performed, depending on the data distribution. Statistical significance will be set to  $p < 0.05$ . The subjective questionnaires will be summarized by visit using descriptive summaries. For numeric measures the change from baseline will be calculated and inferential tests applied. For categorical measures, a shift from baseline will be presented demonstrating the subjects as being better, the same, or worse.

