## **Inclusion and Exclusion Criteria\***

All subjects will be prospectively enrolled for study.

Aims 1 and 2 will include adult English speaking patients who are experienced users of BAIs for the

indication of either single sided deafness or conductive hearing loss. Experienced will be defined as greater than 6 months of device use and no intermittent function of the device within 2 weeks of enrollment. Aims 1 and 2 will require retrospective chart review to identify potential study subjects for recruitment. Subjects who spontaneously present to the clinic may also be enrolled should the meet inclusion criteria. Subjects will be limited to those who have normal hearing by bone conduction defined as a pure tone average of 25 dBHL or better at 500, 1000, 2000, & 3000 Hz in at least one ear.

Aim 3 will include English speaking children 5 to 17 years of age and their primary guardian who present to the clinic for treatment by BAI on a headband device for the indications of single sided deafness or conductive hearing loss. Because subjects for aim 3 have not previously been users of a BAIs, subjects for aim 3 will be recruited during spontaneous presentation to the clinic. Subjects will also be recruited for aim 3 from various sites using flyers and email. Subjects will be limited to those who have no prior use of a BAI or bone conduction hearing device, normal hearing by bone conduction defined as a pure tone average of 25 dBHL or better at 500, 1000, 2000, & 3000 Hz in at least one ear. For those children where this cannot be definitively established, children will be included who display clinical signs of normal bone conduction hearing beyond a reasonable doubt and may include such evidence as (but not limited to): auditory brainstem response, speech awareness thresholds, visual reinforcement audiometry, conditioning play audiometry, CT scans, etc.)

Aims 3 a & b are an extension of Aim 3 and will include pediatric bilateral or unilateral conductive hearing loss patients who are between the ages of 2 and 17 years of age and are currently managed by the UMEI with a bone conduction device attached to a softband will be enrolled for study.

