### **Study Populations**

- Minimum of 10 established adult unilateral profound sensorineural hearing loss recipients of bone anchored implants
- Minimum of 10 established adult conductive hearing loss recipients of bone anchored implants
- Minimum of 10 new pediatric headband bone conductive device candidates.
- Minimum of 10 guardians of the pediatric population involved
- Minimum of 15 established pediatric unilateral conductive hearing loss patients currently fit with a bone conduction device on a softband.
- Minimum of 10 established bilateral conductive hearing loss patients currently fit with a bone conduction device on a softband.

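### The only planned test of hearing performance is tied to transcranial attenuation, an undefined factor, and no test is assigned to Adhear versus its comparator

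*Combined protocol and SAP*

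**What the plan says.** All the analysis text is in the Data Management section of the combined protocol and SAP. On performance it says "Inferential statistics will be applied to detect differences in speech in noise performance as a function of transcranial attenuation". The following sentence offers Student's t-tests for that purpose, or "nonparametric Wilcoxon signed rank tests will be performed, depending on the data distribution", with significance at p < 0.05. After a sentence on summarising the questionnaires comes the only other inferential statement: "For numeric measures the change from baseline will be calculated and inferential tests applied". The list of data collected in the same section includes "aided thresholds, aided speech in noise performance, hours of device use, and subjective outcomes", and transcranial attenuation is not on it.

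The Objectives are about devices. Aim 1 reads "Determine if non-invasive Adhear is an equally effective treatment solution for unilateral profound sensorineural hearing loss when compared to invasive" bone-anchored implants, and Aim 2 says the same for conductive loss. The Aim 3 hypothesis is that Adhear will "increase objective and subjective benefit when compared to traditional bone anchored implant processors worn on a headband". Aim 3b states a comparison with conventional headband systems. The Background also says that objective and subjective outcomes with Adhear will be set against those with conventional implant technology.

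**The concern.** The factor in the test sentence is not device, and it is not a variable the study says it will have. An analyst who followed the sentence literally would run a test that answers none of the aims. The test each aim needs, a within-person comparison of Adhear with its comparator, is not written down for speech in noise, aided thresholds, Ling thresholds, speech reception thresholds (SRT) or word recognition.

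Two things are at stake. First, the contrast is left open where the design allows several. Second, the only decision rule is p < 0.05 on a difference, while Aims 1 and 2 claim equal effectiveness. A non-significant difference could then be taken as support for that claim, which it cannot give.

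**Working it through.** The plan gives no figure on this point to reproduce. The check sets the analysis text against the aims and procedures, then counts.

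**Step 1: the term.** Transcranial attenuation occurs once, in the Data Management test sentence. It is absent from the Objectives, from the procedures for every aim and from the data list. The nearest wording is in Study Design, Aims 1&2, where the processor on a soft headband serves to assess transcutaneous stimulation. That is a different term.

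**Step 2: what the design produces.** Outcomes are taken from the Study Design text and the outcome lists. Data logging is not counted as performance.

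| Aim | Comparator in the design | Performance outcomes | Pairs |
|---|---|---|---|
| 1 | Implant | BKB-SIN, narrowband thresholds, SRT | 3 |
| 2 | Implant | BKB-SIN, narrowband thresholds, SRT | 3 |
| 3 | Traditional device on a headband | Narrowband thresholds, SRT, PBK words | 3 |
| 3a | Child's own headband or softband device | Narrowband thresholds, Ling, SRT, PBK words | 4 |
| 3b | Child's own softband device | Narrowband thresholds, Ling, SRT, PBK words | 4 |

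Total: 3 + 3 + 3 + 4 + 4 = 17 aim-by-outcome pairs.

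**Step 3: how many have an Adhear-versus-comparator test.**
- As written: 0 of 17.
- Reading A, speech-in-noise sentence taken as a device test: BKB-SIN in Aims 1 and 2 (2) plus PBK in 3, 3a and 3b (3) = 5, leaving 17 − 5 = 12.
- Reading B, change-from-baseline sentence taken to cover all numeric outcomes: 4 + 4 = 8 (3a and 3b), leaving 17 − 8 = 9.
- A and B together: PBK in 3a and 3b falls under both, so 5 + 8 − 2 = 11, leaving 17 − 11 = 6. These are narrowband thresholds and SRT in Aims 1, 2 and 3.

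**Step 4: why Reading B stops at 3a and 3b.** In 3a the group is "Minimum of 15 established pediatric unilateral conductive hearing loss patients currently fit with a bone conduction device on a softband", and Visit 1 tests that device, so baseline is the comparator. Aim 3b starts in the same way. In Aims 1 and 2 the implant and Adhear are both tested at the first session, so a baseline does not identify one device. In Aim 3, "Subjects will be limited to those who have no prior use of a BAI or bone conduction hearing device", so a baseline before assignment is not the headband device, and no visit is given for the performance measures. Eight is generous for 3b. Most of those children are expected to have one device at Visit 1, and the bilateral softband condition comes at Visit 3 or 4. Change from Visit 1 then gives no like-for-like bilateral contrast.

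**Step 5: contrasts left open.** In Aims 1 and 2 Adhear is measured at two sessions. There are two other conditions: the implant at the first session and the processor on a soft headband after the trial. Each outcome allows 2 × 2 = 4 Adhear contrasts, and none is designated. Aim 3b adds unilateral or bilateral fitting.

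**Step 6: sensitivity of the count.** The 3a and 3b lists place noise in front but give no noise level. If PBK there is not speech in noise, Reading A falls to 3, but A and B together are still 3 + 8 = 11, leaving 6. Counting data logging in 3, 3a and 3b raises the total to 20, and the literal count stays at none.

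**The case against.** The strongest reply is that the intention is clear. The Background and Objectives say devices will be compared, Aims 1 and 2 test implant and Adhear in the same person with conditions randomised, and the signed rank test is a paired test. On that view transcranial attenuation is a slip of wording and a reader can recover the contrast. Most of this stands: a paired device comparison was probably intended. It does not supply the test, because none of those statements names an outcome, visit or pairing, and the one sentence that names a test gives another factor.

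A second reply is that change from baseline could reach further than 3a and 3b. In Aims 1 and 2 one could take the first-session implant score as baseline for Adhear after the trial. That would bring in four more pairs and leave 6 − 4 = 2, both in Aim 3. However, the plan does not define baseline that way, first-session Adhear is an equally available baseline, and the sentence follows directly on the questionnaires.

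Third, attenuation might be derivable from the audiometric thresholds. No derivation is given, and it would still not answer an aim.

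A reader might also infer that the contrast would be picked after the data are seen. The documents leave it open but do not say when it would be chosen, so that is a risk and not a finding.

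**Conclusion.** The point holds. The plan's only performance test names a factor that the study neither defines nor collects, so the sentence is wrong as written and not merely short of detail. No performance outcome has an assigned Adhear-versus-comparator test: 0 of 17 literally, and 6 of 17 still uncovered when both charitable readings are granted together. The count assumes that data logging is not a performance outcome and that a first session containing both devices does not define a baseline device.

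Two stronger readings are not supported. One is that the study plans no device comparison; the Background and Objectives state that intention, and the gap is in the planned test. The other is that the adult groups are capped at a small size, so that this point also shows inadequate power. The recruitment text allows up to 30 per study group. The group minima sum to 55 without guardians and 65 with them, against a local total of 60, so no ceiling can be derived. The choice of a single primary outcome per aim is a separate multiplicity question and is not needed here.

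**What to change.** Before analysis, replace the test sentence in Data Management with: *Speech in noise and the other performance outcomes will be compared within subject between Adhear and the comparator of each aim.* Keep the tests already named, specifying the paired t-test or the Wilcoxon signed rank test. Then add:

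- **Comparator:** the implant in Aims 1 and 2; the traditional device on a headband in Aim 3, with the analysis allowing for period in the two-phase crossover; the child's own headband or softband device in 3a and 3b.
- **Visit and fitting for each contrast:** first-session or post-trial Adhear in Aims 1 and 2; the visit at which performance is measured in Aim 3; unilateral or bilateral fitting in 3b.
- **Soft-headband condition in Aims 1 and 2:** its role in the analysis. The procedures give it a purpose but no analysis.
- **Transcranial attenuation:** define it, with its derivation from collected data, as a secondary analysis, or delete it.
- **Aims 1 and 2:** report the paired difference with a 95% CI and state that p ≥ 0.05 is not evidence of equal effectiveness.

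The cost is one rewritten paragraph and no new data. The Aims 1 and 2 conclusions may have to be worded as estimates. The choice of session also has a price. The first session sets experienced implant users against Adhear before its home trial, and the later session compares measurements made on different days.
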